6.4 Qualitative Data

Qualitative process evaluation data will be gathered to examine patients' and clinicians' perceptions of the TCM and IPT interventions; to describe the context and processes of intervention delivery; and to assess potential for long-term sustainability and widespread dissemination of the interventions.

6.4.1 In depth interviews with patient participants, clinician participants, and other VA employees

A purposeful sample of patient participants in both the TCM and IPT intervention arms will be interviewed by telephone after their study participation is complete. We will purposefully select participants who are diverse in terms of age, sex, race/ethnicity, study site, and level of participation in the intervention (defined by the number of intervention visits completed during 12 months). The data team will provide names of potential participants based on demographic characteristics, assigned arm, and level of participation; interviews will take place within approximately three months after completing the study intervention. A semi-structured interview guide will be used. Questions will address experiences with the interventions, perceptions of the value and convenience of the interventions, what (if any) aspects of the intervention were most or least influential in terms of their personal treatment outcomes, and any recommendations for improvements. Interviews will be audio-recorded and transcribed. Data collection will continue until theoretical saturation is reached. Based on recommendations for qualitative sampling, we expect to conduct 15 interviews for each study arm, for a total of approximately 30 patient interviews.

In addition, a separate sample of VOICE participants across both intervention arms will be interviewed by telephone about COVID-19 pandemic-related experiences that could be relevant to their pain and pain care. Interviews will be conducted using an original semi-structured interview guide following the same approach described above for other patient interviews. We anticipate conducting approximately 30 additional interviews.

A purposeful sample of clinician participants will be interviewed. Intervention clinicians at different sites, in both arms, and with differing roles will be asked to participate. Interviews will be one-time events and will be timed to obtain information about intervention implementation; therefore, they may be done before, during, or after intervention participation. Interview questions will address reactions to the intervention, perceptions of effects of the intervention on patient outcomes, key facilitators and barriers to maintaining the interventions as standard clinical practice, and recommendations for changes to the intervention to increase the "fit" of the intervention into the clinic. Clinicians will also be asked about effects of increased use of telehealth. To inform possible future implementation efforts, the interviews will also focus on perceptions of the facilitation method for implementation of the interventions in order to determine whether the level of facilitation was sufficient for high fidelity implementation, whether it created an undue burden on clinical personnel and any changes that could be made to improve facilitation.

In addition, up to 46 VOICE clinicians involved in discussing buprenorphine as part of the expanded taper options intervention will be interviewed about their perspectives on buprenorphine and experiences with discussing buprenorphine. Buprenorphine-related clinician interviews are expected to take 30-60 minutes. If clinicians are also completing

the main interview described above, buprenorphine-related interview questions may be asked at the same session or at a second separate interview session, depending on logistics and the preferences of the clinician being interviewed.

Finally, selected additional local site clinicians, administrative staff, and other VA employees will be interviewed during the study as part of the process evaluation. These additional VA employees will be selected based on their positions and experience with the study, with the goal of obtaining a diverse array of perspectives on intervention implementation processes. Unlike the patient participants and clinical participants described above, these employees will not have prior participation in the study. Study investigators will identify potential participants and Minneapolis coordinating center personnel will send invitations by email. Employees who agree to schedule an interview will be informed of the study purpose using an information sheet, provided the opportunity to have questions answered, and asked to provide verbal consent. Interview questions will address facilitators and barriers to maintaining the interventions as standard clinical practice, recommendations for changes to the intervention to increase the “fit” of the intervention into clinical practice, burden on clinical personnel, and any changes that could be made to improve implementation.

6.4.2 Informal interviews and observation

The study process evaluation team will collect data on study implementation processes using participant observer and unstructured conversational interview techniques. They will attend and observe meetings, including investigator meetings, local site rollout meetings, and intervention clinician team meetings. In the context of these meetings and other interactions, they will gather data from investigators, intervention clinicians, and stakeholders using unstructured conversational interview questions. Data will be recorded in the form of field notes.

7. STATISTICAL ANALYSIS

7.1 Sample Size Considerations

For our power calculations, we used an effective sample of at least 776 patient participants (at least 80% of initial sample size of 970) for the comparison of 12-month outcomes.

7.1.1 Power estimates for primary analyses

Prior research observed 50% of patients achieving a 30% or greater reduction in BPI at one year with a TCM intervention. Assuming a similar response rate for TCM at a significance level of 0.05, a sample size of 970 enrolled participants provides 80% power for a 2-sided chi-squared test comparing pain response rates for TCM and IPT if IPT adds 10% to the response rate, and > 85% power if IPT adds 11% to the response rate. For the second aim examining adding buprenorphine to the tapering protocol, with an unadjusted 0.05 significance level, the estimated proportion of the sample on high-dose therapy (35%) will result in approximately 135 participants per treatment group and provide > 80% power to detect small to moderate effects (Cohen d or standardized difference) in mean BPI scores of 0.35 or more.

7.1.2 Subgroup power estimates

A difference of 1 unit in BPI is considered clinically significant and the SD of the BPI scores is typically about 2 units. A sample size of 776 participants at the 12-month

assessment will provide $> 80\%$ power for detecting a clinically meaningful difference in intervention effects across subgroups with prevalence of at least 40%, assuming a Bonferroni corrected significance level of 0.01. For a 1.2-unit difference in intervention effects, the study will have $> 85\%$ power for subgroup prevalence of 25% or more. Within a subgroup, the study will have $> 80\%$ power to detect an intervention effect of 1 unit or more for subgroup prevalence of $> 25\%$ and a 0.01 significance level. These power calculations for comparisons of 12-month outcomes consider just the data for this assessment point as a worst-case scenario. The repeated measures analyses discussed below should have power greater than discussed here for comparing the 12-month outcomes. Based on preliminary data, we anticipate the proposed sample size will provide adequate power for planned assessments of the HTE for all planned subgroups; if prevalence of any subgroup is $< 25\%$, assessment of HTE across subgroups will be exploratory.

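### Interaction power and the exploratory rule in section 7.1.2 set only a lower prevalence limit, although power falls equally as a subgroup becomes very common

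*Combined protocol and SAP*

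**What the plan says.** Section 7.1.2 starts from the premise that "A difference of 1 unit in BPI is considered clinically significant and the SD of the BPI scores is typically about 2 units". With 776 patients at 12 months it then makes three claims at a significance level of 0.01:

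- More than 80% power for a 1-unit "difference in intervention effects across subgroups with prevalence of at least 40%, assuming a Bonferroni corrected significance level of 0.01".
- Power above 85% when subgroup effects differ by 1.2 units, again with only a lower prevalence limit, here 25%.
- More than 80% power for an effect of 1 unit within a subgroup whose prevalence is above 25%.

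The section describes these figures as a worst case because they use the 12-month data alone. It expects "adequate power for planned assessments of the HTE for all planned subgroups", citing preliminary data that are not shown. If a subgroup's prevalence is below 25%, "assessment of HTE across subgroups will be exploratory".

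Section 7.1.1 puts the high-dose share at 35%. No prevalence is given for the depression, post-traumatic stress, substance use or fibromyalgia subgroups. Section 7.4 tests each interaction with a two-sided Wald test at 0.005 and adjusts for baseline BPI.

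**The concern.** An interaction test compares the treatment effect in patients with a characteristic against the effect in patients without it. Its precision is governed by the smaller of the two groups, whichever that is. A condition present in 85% of patients leaves a 15% comparison group and gives exactly the power of a condition present in 15%. Under section 7.1.2 the second is demoted to exploratory and the first is not.

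What is at stake is how a null result is read. If one of the symptom subgroups turns out to be very common, a non-significant interaction would fall under the plan's statement of adequate power although the comparison group was too small to support it. Section 10.4.2 expects a substantial burden of physical and mental comorbidity, and section 1.2.1 defines the subgroups only as present or absent, without cut-offs, so the documents do not let a reader bound their size.

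**Working it through.** **Inputs.** N = 776 (section 7.1, 80% of 970). SD = 2 and differences of 1 and 1.2 units (section 7.1.2). Equal allocation to TCM and IPT within dose strata (section 4.3.9). Two-sided alpha 0.01 (section 7.1.2), with 0.005 (section 7.4) as the alternative.

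**Formula.** With prevalence p and equal arms, the standard error of the difference in treatment effects is

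SE = SD × √[4/(Np) + 4/(N(1-p))] = 2·SD / √[N·p(1-p)]

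Power = Φ(δ/SE - z), with z = 2.576 at alpha 0.01 and 2.807 at 0.005.

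**Reproducing the plan's figures.**

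- 1 unit at 40%: SE = 4/√(776 × 0.24) = 0.293; 1/0.293 = 3.412; Φ(3.412 - 2.576) = 79.8%. Stated: more than 80%, so this agrees within rounding.
- 1.2 units at 25%: SE = 4/√(776 × 0.1875) = 0.332; 1.2/0.332 = 3.619; Φ(3.619 - 2.576) = 85.1%. Stated: more than 85%.
- 1 unit within a 25% subgroup (97 per arm): SE = 2√(2/97) = 0.287; Φ(3.482 - 2.576) = 81.8%. Stated: more than 80%.

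All three reproduce at their lower limits, so this is evidently the calculation behind the section.

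**The same formula across prevalence (unadjusted, N = 776).**

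| Prevalence | 1 unit, 0.01 | 1.2 units, 0.01 | 1 unit, 0.005 | 1.2 units, 0.005 |
|---|---|---|---|---|
| 50% | 81.8% | 94.5% | 75.0% | 91.5% |
| 40% or 60% | 79.8% | 93.6% | 72.7% | 90.1% |
| 35% or 65% | 77.2% | 92.1% | 69.7% | 88.1% |
| 30% or 70% | 73.1% | 89.5% | 65.0% | 84.7% |
| 25% or 75% | 67.0% | 85.1% | 58.3% | 79.2% |
| 20% or 80% | 58.3% | 77.8% | 49.1% | 70.4% |
| 15% or 85% | 46.4% | 65.8% | 37.4% | 57.0% |

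At alpha 0.01, 80% power for 1 unit needs p between 40.4% and 59.6%, and 85% for 1.2 units needs p between 24.9% and 75.1%. At alpha 0.005, no prevalence gives 80% for 1 unit, and 85% for 1.2 units needs about 30% to 70%.

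**High-dose subgroup (35%).** At alpha 0.01, unadjusted interaction power is 77.2% for 1 unit and 92.1% for 1.2 units. Within-subgroup power for 1 unit is 93.9%.

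**Allowing for the worst-case caveat.** The baseline correlation is not in the documents. I assume 0.3 to 0.6, which scales the SD by √(1-ρ²). At alpha 0.01 and N = 776, 1-unit power becomes 81.8-94.3% at 35% or 65%, 72.1-88.4% at 75%, 63.5-81.8% at 80%, and 51.2-70.3% at 85%. With 95% retention instead (0.95 × 970, about 922) and no adjustment, it is 85.2% at 35% or 65% and 76.2% at 75%. With that retention and a correlation of 0.6 together, it is 79.2% at 85%.

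**The case against.** Four points can be made for the plan.

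**The upper-end failure is hypothetical.** The only prevalence given is 35%. A substantial comorbidity burden is not a prevalence, and section 4.2 excludes unstable or severe untreated psychiatric disorder. This stands: the documents do not show that any subgroup will exceed 60%. It does not rescue the rule, which treats two equally powered cases differently whatever the true prevalences are.

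**The figures are a declared worst case.** Section 7.1.2 says the repeated-measures analysis should do better, section 7.4 adjusts for baseline BPI, and section 7.2 reports completion above 95% in similar studies. This largely stands at 65-75%, where plausible adjustment or retention could restore 80%. At 85% the most favourable combination tried still falls just short.

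**The high-dose subgroup.** A reader might infer that the claim of more than 80% power is false for this subgroup. The documents do not support that. The claim starts at 40%, and the two claims that do cover 35% hold (92.1% and 93.9%). What remains is that the expectation of adequate power for every subgroup names no effect size, and 1-unit interaction power at 35% is 77.2%.

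**The 25% cut.** A reader might also infer that it has no basis in the 1-unit difference. It does: it matches the 1-unit within-subgroup claim (81.8%). It fails to match only the 1-unit interaction claim, where power at 25% is 67.0%.

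**Conclusion.** The concern holds in a limited form. The two interaction claims are right at their lower limits but wrong as open-ended statements: on the plan's inputs at alpha 0.01 they hold only for about 40-60% (1 unit) and about 25-75% (1.2 units). The exploratory rule omits the mirror-image case of a comparison group below 25%. The loss of power rests on a subgroup actually being that common, which no document states, and on unadjusted 12-month data; the one-sidedness of the rule rests on neither.

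The two significance levels also need to be reconciled. At the 0.005 that section 7.4 applies, unadjusted 1-unit interaction power peaks at 75.0%, so simply adding upper limits to the present figures would still misstate power for the planned test.

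It would go too far to conclude that the subgroup analyses are underpowered in general, or that the plan treats them as confirmatory; it never uses that word for them. The issue concerns heterogeneity analyses and affects neither the sample size nor the primary test.

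**What to change.** In section 7.1.2, with a matching change in section 7.4:

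1. Make heterogeneity exploratory when the smaller of the two groups, with or without the characteristic, is below 25% of the sample.
2. Give both prevalence limits for each interaction claim. At alpha 0.01 these are about 40-60% for 1 unit and 25-75% for 1.2 units.
3. Tie the statement of adequate power to a named difference, such as 1.2 units (92% for the high-dose subgroup at 35% and alpha 0.01), and report 77% for 1 unit there.
4. Use one significance level in both sections and compute the restated figures at it. If 0.005 is kept, unadjusted 1-unit power is at most 75.0% (72.7% at 40%, 69.7% at 35%). For 1.2 units it is 79.2% at 25% or 75%, and exceeds 85% only for about 30-70%.

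If the plan wants credit for baseline adjustment or better retention, it should state the correlation and completion rate assumed. The cost is a few sentences and slightly less favourable stated figures; no design change is needed.

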7.2 General Analytic Approach

We will use an intent-to-treat approach, including all patient participants in the arm to which they were originally assigned. Preliminary descriptive analyses will summarize the distributions of the relevant baseline measures for each arm together with outcome distributions across the assessment points. We will summarize completeness of the outcome assessments and examine associations between completeness and the baseline measures as well as pain measurements, receipt of pain medicines outside the VA, and VA service utilization over the follow-up period. In previous and ongoing studies using similar eligibility criteria and follow-up structure, we have observed outcome completion rates in excess of 95% at each assessment time-point and $> 98\%$ of participants have provided outcomes at one or more follow-up time-points. Initial analysis will use all available follow-up data and subsequent sensitivity analyses will examine the potential effect of response bias.

7.3 Statistical Analysis of Primary Aim

We will use all follow-up data in a repeated-measures logistic regression modeling 30% reduction from baseline in BPI scores at the quarterly follow-up assessments. The regression model will use assigned intervention, assessment point, and their interaction as explanatory measures. Assessment points will be incorporated as random effects, with non-zero means and an unstructured covariance, to model potential correlation among outcomes for individuals. Our primary assessment of intervention effects will examine differences in the log odds of attaining a 30% reduction in BPI at the 12-month assessment using a two-sided Wald test (0.05 significance level), together with the corresponding model-based odds ratio point and confidence interval estimates.

To assess the sensitivity of these initial analyses to response bias, we will fit a series of weighted selection model analyses. Each analysis will use an EM algorithm to estimate weights to assign to potential values of the missing outcomes for use in logistic regression. The regression will model the log odds of a reduction in BPI at 12 months using the assigned intervention and relevant baseline measures as predictors. The EM algorithm will jointly use a logistic model for observation of the 12-month outcome to iteratively update the weight estimates. These latter logistic models will be varied to use different combinations of the following variables—12-month outcome, intervention, observation and value of the outcome at prior assessments, and baseline covariates together with pain measurements and services utilization over the follow-up period—as predictors to consider different potential missing at

random and missing not at random mechanisms generating the missing data. The approach outlined above will also be used to examine differences in reduction in opioid use at 12 months, the combination of pain reduction and opioid use reduction, and the BPI severity and interference subscales.

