4.3.9 Randomization

After obtaining the written informed consent document (either in person or upon receipt of the original mailed copy) and completing the baseline interview, the local site coordinator/research assistant will initiate randomization using the study application randomization form. The randomization code will not be visible to personnel conducting randomization and can be completed only once per study ID, preventing study personnel from influencing treatment allocation. This process will simultaneously inform the coordinator and participant of the primary study arm assignment. To prevent patients from feeling pressured to taper opioids, the taper option assignment will be revealed only when participants agree to discuss options for opioid dose reduction. Regardless of whether the taper intervention is delivered, participants will be evaluated in their assigned arm.

Patients will be randomized within site and opioid dose (i.e., moderate or high) categories, in permuted blocks of size 4 or 8, to balance the proportions of participants with moderate-dose and high-dose opioid therapy in the intervention arms. Those in the moderate-dose group will be randomly assigned, with equal likelihood, to intervention arms. Those in the high-dose group will be randomly assigned, with equal likelihood, to intervention and tapering strategy combinations.

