7.4 Pre-Specified Subgroup Analyses

We will examine variation in the intervention effects on the change in BPI within clinical subgroups defined by presence or absence at baseline of the subgroup status/conditions described above. For each subgroup measure, we will fit a repeated-measures linear regression modelling change from baseline in BPI at the quarterly follow-up assessments using assigned intervention, assessment point, subgroup indicator and all interactions between these three measures together with baseline BPI score and its interaction with assessment point as explanatory measures. Assessment points will be incorporated as random effects, with an unstructured covariance, to model potential correlation among outcomes for individuals. Our primary assessment of an interaction between intervention and the subgroup measure will use the model-based two-sided Wald test for an interaction at the 12-month assessment, using a 0.005 significance level. Weighted selection model analyses similar to those described above will examine sensitivity of 12-month results to response biases.

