7.5 Secondary Analyses and Analysis of Secondary Outcomes

If the proportion of patients in the standard options arm achieving the 50% dose reduction outcome falls in the range 20%-70%, the anticipated sample size will provide 80% power to detect between-group differences in the range of 14 and 17%. The study will have this same level of power for comparable differences in the proportions achieving a 25% dose reduction and proportions with any dose reduction. We will have 80% power for assessing small to moderate differences of 0.35 SD in mean dose change.

The secondary dose escalation outcome is defined as a proportional increase in daily dose of $\geq 25\%$ from baseline to 12 months. If 5-15% of participants meet this dose escalation outcome, we will have 80% power to detect between-group differences of 7-8%.

In addition, we will assess between-group differences in the pain-related function, pain intensity, quality of life, fatigue and sleep, mental health measures, and physical symptoms over the follow-up period. We will fit separate repeated-measures linear regressions modelling change from baseline at the follow-up assessments using assigned intervention, assessment point and their interaction together with the respective baseline score and its interaction with assessment point as explanatory measures. Assessment points will be incorporated as random effects, with an unstructured covariance, to model potential correlation among outcomes for individuals. The primary assessment of an intervention effect on a particular outcome will use the model based 2-sided Wald test for a difference at the 12-month assessment together with the point and confidence interval estimates for the mean difference in change from baseline.

We will examine variation in effects by sex, study site and over the course of enrollment, as well as moderation of effects by relevant covariates. Analyses will be similar to the subgroup analyses described above.

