7.6 Analysis of Tapering Strategies

Among the subset of participants on high-dose opioid therapy at baseline we will modify the analyses discussed above by adding the tapering assignment as an explanatory measure to the

model structure in the same manner as the TCM/IPT measure is included in the models. We will use comparable testing and estimation approaches to assess whether the expanded tapering option results in better outcomes in this subpopulation.

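### The primary logistic model omits the randomisation strata (site, dose category) and baseline BPI; it stays valid but gives up about 0 to 3 points of power

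*Combined protocol and SAP*

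**What the plan says.** Section 4.3.9 sets the strata: "Patients will be randomized within site and opioid dose (i.e., moderate or high) categories, in permuted blocks of size 4 or 8". Within the high-dose category, patients are allocated equally across the four combinations of intervention and taper strategy, so taper assignment is also randomised within site.

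Section 7.3 specifies the primary model: "The regression model will use assigned intervention, assessment point, and their interaction as explanatory measures". Correlation over time is handled as follows: "Assessment points will be incorporated as random effects, with non-zero means and an unstructured covariance". The test is a two-sided Wald test of the 12-month log odds at 0.05. No other section adds site, dose category or baseline BPI to this model, and 7.3 extends the same approach to opioid reduction, the composite and the BPI subscales.

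Other models treat the baseline score differently. The subgroup models in 7.4 fit their terms "together with baseline BPI score and its interaction with assessment point as explanatory measures", and the secondary-outcome models in 7.5 do so "together with the respective baseline score and its interaction with assessment point as explanatory measures". The 12-month selection-model regressions in 7.3 are fitted "using the assigned intervention and relevant baseline measures as predictors", but those measures are not named. For Aim 2, section 7.6 says "we will modify the analyses discussed above by adding the tapering assignment as an explanatory measure to the" existing models.

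Site appears only as a possible source of variation in effect (1.2.3 and the last paragraph of 7.5). Dose appears only as a subgroup factor (1.2.1, 7.4).

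**The concern.** Stratified randomisation balances the arms on site and dose. If those factors predict response, that balance makes the treatment comparison more precise, but a model without the strata does not use the gain. Its standard error is somewhat too large, so the test is conservative and power is lost. Baseline BPI may offer a further gain for the same reason.

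A second, smaller matter is interpretation. The primary odds ratio comes from a model with random effects and is therefore subject-specific. The selection-model regression is a 12-month logistic model with no random effects described, and it uses unnamed covariates. The two odds ratios can differ through scale and covariates alone, even if missing data cause no bias. A reader could take that difference for response bias, which is what the sensitivity analyses are meant to detect.

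**Working it through.** **Inputs from the protocol.** 970 enrolled, 80% assumed evaluable, so 776 or 388 per arm (7.1). Response 50% under TCM against 60% under IPT, two-sided 0.05, and 35% on high dose (7.1.1). Ten sites. Permuted blocks of 4 or 8 within site by dose (4.3.9). On completion in similar studies, 7.2 says "we have observed outcome completion rates in excess of 95% at each assessment time-point".

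**The plan's own figure.** Pooled-variance power is Φ[(δ − 1.96·√(2p̄q̄/n)) / √((p₁q₁ + p₂q₂)/n)].

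- √(2 × 0.55 × 0.45 / 388) = 0.03572, and √((0.25 + 0.24) / 388) = 0.03554.
- (0.10 − 1.96 × 0.03572) / 0.03554 = 0.844, giving **80.1%**. The unpooled form is 0.10/0.03554 − 1.96 = 0.854, giving 80.3%.
- For an 11-point difference, power is 87.1%, in line with the plan's figure of more than 85%.
- At 95% completion, 970 × 0.95 / 2 ≈ 461 per arm, and power is 86.4% (pooled) or 86.6% (unpooled).

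The sample size therefore does not depend on covariate adjustment.

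**First-order gain.** If covariates explain a share R² of outcome variance, the effective size is about 388/(1 − R²) per arm. Power for 50% against 60% is then 80.5% at R² = 1%, 81.3% at 3%, 82.1% at 5% and 84.0% at 10%.

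**Simulation.** 20,000 trials per scenario: 970 enrolled, 10 equal sites, 35% high dose, blocks as in 4.3.9, outcomes missing at random, marginal response 50% against 60% (50% in both arms under the null), and a 12-month logistic regression with a Wald test. Covariate strengths are assumptions:

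| Scenario | Site SD (logit) | Dose log OR | Baseline BPI, log OR per SD | R² (strata alone) |
|---|---|---|---|---|
| None | 0 | 0 | 0 | 0 |
| Mild | 0.2 (about 5 points) | −0.2 | 0.3 | 3.2% (1.2%) |
| Moderate | 0.4 (about 10 points) | −0.4 | 0.4 | 7.6% (4.5%) |

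Power (%), and type I error without covariates:

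| Scenario | Observed | No covariates | + site, dose | + baseline BPI | Total gain | Type I error, no covariates |
|---|---|---|---|---|---|---|
| None | 80% | 79.5 | 79.8 | 79.8 | 0.3 | 4.9% |
| Mild | 80% | 80.4 | 81.0 | 81.8 | 1.4 | 4.7% |
| Moderate | 80% | 80.4 | 81.9 | 83.3 | 2.9 | 4.4% |
| Mild | 95% | 86.5 | 87.1 | 87.7 | 1.2 | – |
| Moderate | 95% | 87.0 | 88.0 | 88.9 | 1.9 | – |

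Monte Carlo standard error is about 0.3 points for power and 0.15 for type I error, so the 0.3 in the first row is about the size of simulation error. At 80% observed, the strata account for 0.6 (mild) and 1.5 (moderate) points of the gain. Adjusted type I error is 4.9 to 5.0%.

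A separate run of 2,000 trials per scenario, with different assumed strengths, showed gains of about 0 to 3 points for none-to-strong effects (site SD up to 0.4, dose −0.5, BPI 0.5). Only a very strong baseline effect (site SD 0.5, dose −0.5, BPI 0.8 per SD) gave more: 81.0% to 86.4%.

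**How predictive baseline BPI could be.** The outcome is a percentage reduction, so baseline is already built into it. Assuming a baseline mean of 6.5, baseline SD of 1.3 to 2.0, follow-up SD of 2 and baseline-to-12-month correlation of 0.3 to 0.7, baseline BPI alone explained 0% to 9% of response variance, with a log odds ratio per SD between −0.55 and 0.65.

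**Scale of the odds ratio.** 50% against 60% is a marginal odds ratio of (0.6/0.4)/(0.5/0.5) = 1.50. Conditioning on the simulated covariates moves it to 1.53–1.56. For random effects, the usual approximation is subject-specific log OR = marginal log OR × √(1 + 0.346 × variance):

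- variance 1: 0.4055 × √1.346 = 0.470, OR 1.60;
- variance 4: 0.4055 × √2.384 = 0.626, OR 1.87.

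The variances are assumed, since the plan gives none.

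**The case against.** Nothing in the plan is wrong in the strict sense. The test holds its level, the power calculation reproduces, and the gain rests on covariate strengths that the documents do not supply. With no prognostic effect the gain is nil, so the fair range is about 0 to 3 points. This stands, and it limits how strongly the change can be urged.

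The simulation uses one time point, whereas the plan fits all quarterly data with random effects, and 7.1.2 expects more power from that. This also stands: the figures show the order of the gain, not its exact value. No gain was computed for Aim 2, whose primary outcome is a mean.

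The baseline adjustment in 7.4 and 7.5 belongs to change-score models, where the case for it is stronger than for a percentage-reduction responder. That is a fair distinction, and baseline BPI may add little. It does not affect the argument for the strata.

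Adding covariates to a logistic model also changes what the odds ratio estimates. That is true, and the shift from 1.50 to 1.53–1.56 is small. It is a reason to fix the covariates in advance and state the scale.

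Finally, site and dose do appear elsewhere in the plan. They enter as effect modifiers in separate analyses, which does not put them into the primary model.

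**Conclusion.** The omission is real and its consequence is small. The planned primary analysis is valid, and slightly conservative if the strata predict response (simulated type I error down to 4.4%). Adjustment would recover about 0 to 3 points of power at 776 observed: 1.4 to 2.9 under the mild and moderate assumptions, and none if the covariates are uninformative. At 95% completion the range under the same assumptions is 1.2 to 1.9 points.

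These results assume missingness unrelated to the omitted variables. If completion depends on site, dose or baseline BPI, the model without them also needs a stronger missing-at-random assumption; that effect was not quantified. The change is advisable because it matches analysis to design at little cost. The trial's conclusions do not hinge on it.

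**What to change.** - **7.3, primary model:** add site, dose stratum as randomised, and baseline BPI with its interaction with assessment point, as fixed terms. Keep the odds ratio and the two-sided Wald test at 12 months as primary, and state that the odds ratio is conditional on the covariates and the random effects.
- **7.3, selection models:** name the same covariates for the 12-month outcome regression.
- **7.6:** keep site in the Aim 2 models. Dose stratum is constant there, because only high-dose patients are included.
- **Supplement only:** report a standardised marginal 12-month risk difference or odds ratio from both the primary and the sensitivity models, so that they can be compared on one scale.

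**Cost.** No new data. The model gains 14 fixed parameters (9 site, 1 dose, 1 baseline BPI, 3 for its interaction with assessment point) with at least 776 participants. With random effects at four assessment points, it is worth stating what will be done if the fit does not converge. The marginal estimate needs one extra programming step to integrate out the random effects. The wording change needs Central IRB approval as an amendment (10.8.1), and a funder request if it is judged a significant change of methodology (10.8.3.4). It should be settled before outcomes are seen by arm.
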